11.5.2 Safety

Vital signs

All vital signs data will be listed by treatment group, patient, and visit/time and if ranges are available abnormalities (and relevant orthostatic changes) will be flagged. Summary statistics will be provided by treatment and visit/time.

ECG evaluations

All ECG data will be listed by treatment group, patient and visit/time, abnormalities will be flagged. Summary statistics will be provided by treatment and visit/time.

Clinical laboratory evaluations

All laboratory data will be listed by treatment group, patient, and visit/time and if normal ranges are available abnormalities will be flagged. Summary statistics will be provided by treatment and visit/time.

Adverse events

All information obtained on adverse events will be displayed by treatment group and subject.

The number and percentage of patients with adverse events will be tabulated by body system and preferred term with a breakdown by treatment. A patient with multiple adverse events within a body system is only counted once towards the total of this body system.

11.5.3 Pharmacokinetics

BAF312 plasma concentration data will be listed by treatment, patient, and visit/sampling time point.

Commercially Confidential Information

11.5.4 Pharmacokinetic / pharmacodynamic interactions

Not applicable.

11.5.5 Other assessments

Not applicable.

11.6 Analysis of exploratory variables

Commercially Confidential Information

Commercially Confidential Information

11.7 Sample size calculation

Based on the literature ([Staykov et al 2011](#); [Volbers et al 2011](#)), the reported variability (Coefficient of Variation, CV) of absolute PHE volume in ICH patients within first 12 to 16 days of ICH is in the range 70% to 92%, and that of relative PHE is in the range 64% to 114%. Assuming a CV of 90%, the design with 60 evaluable patients expected to have data on aPHE at day 14 (30 on BAF312 and 30 Placebo) has 80% power to detect statistically significant treatment difference at 1-sided $\alpha=0.05$, when the true mean percent reduction in PHE at a given time point (BAF312 over Placebo) is 40%.

11.8 Power for analysis of key secondary variables

Not applicable.

11.9 Interim analyses

Commercially Confidential Information

12 Ethical considerations

12.1 Regulatory and ethical compliance

This clinical study was designed and shall be implemented and reported in accordance with the International Conference on Harmonisation Harmonized Tripartite Guidelines for Good Clinical Practice, with applicable local regulations (including European Directive 2001/20/EC, US CFR 21, and Japanese Ministry of Health, Labor, and Welfare), and with the ethical principles laid down in the Declaration of Helsinki.

12.2 Responsibilities of the investigator and IRB/IEC

Before initiating a trial, the investigator/institution must obtain approval/favorable opinion from the Institutional Review Board/Independent Ethics Committee (IRB/IEC) for the trial protocol, written informed consent form, consent form updates, patient recruitment procedures (e.g. advertisements) and any other written information to be provided to patients. Prior to study start, the investigator is required to sign a protocol signature page confirming his/her agreement to conduct the study in accordance with these documents and all of the instructions and procedures found in this protocol and to give access to all relevant data and records to Novartis monitors, auditors, Novartis Quality Assurance representatives, designated agents of Novartis, IRBs/IECs,

and regulatory authorities as required. If an inspection of the clinical site is requested by a regulatory authority, the investigator must inform Novartis immediately that this request has been made.

For this multi-center trial, a Coordinating Investigator will be selected by Novartis by the time of Last Patient Last Visit to be a reviewer and signatory for the clinical study report.

12.3 Publication of study protocol and results

The key design elements of this protocol will be posted in a publicly accessible database such as clinicaltrials.gov. In addition, upon study completion and finalization of the study report the results of this trial will be either submitted for publication and/or posted in a publicly accessible database of clinical trial results.

12.4 Quality Control and Quality Assurance

Novartis maintains a robust Quality Management (QM) system that includes all activities involved in quality assurance and quality control, including the assignment of roles and responsibilities, the reporting of results, and the documentation of actions and escalation of issues identified during the review of quality metrics, incidents, audits and inspections.

Audits of investigator sites, vendors, and Novartis systems are performed or overseen by Novartis Pharma Auditing and Compliance Quality Assurance (or CRO working on behalf of Novartis), a group independent from those involved in conducting, monitoring or performing quality control of the clinical trial. The clinical audit process uses a knowledge/risk based approach.

Audits are conducted to assess GCP compliance with global and local regulatory requirements, protocols and internal SOPs, and are performed according to written Novartis processes.

13 Protocol adherence

This protocol defines the study objectives, the study procedures and the data to be collected on study participants. Additional assessments required to ensure safety of patients should be administered as deemed necessary on a case by case basis. Under no circumstances is an investigator allowed to collect additional data or conduct any additional procedures for any research related purpose involving any investigational drugs under the protocol.

Investigators ascertain they will apply due diligence to avoid protocol deviations. If an investigator feels a protocol deviation would improve the conduct of the study this must be considered a protocol amendment, and unless such an amendment is agreed upon by Novartis and approved by the IRB/IEC and health authorities, where required, it cannot be implemented. All significant protocol deviations will be recorded and reported in the CSR.

ALT or AST elevation accompanied by symptoms	
 ALT or AST > 3 × ULN accompanied by (general) malaise, fatigue, abdominal pain, nausea, or vomiting, or rash, or eosinophilia
Isolated ALT or AST elevation	
 ALT or AST > 8 × ULN 5 × ULN < ALT/AST ≤ 8 × ULN 3 × ULN < ALT/AST ≤ 5 × ULN
Isolated ALP elevation	
 ALP > 2 × ULN (in the absence of known bone pathology)
Others	
 Any clinical event of jaundice (or equivalent term) Any adverse event potentially indicative of liver toxicity

Table 15-2 Actions required for Liver Events

Criteria	Actions required
Potential Hy's Law case	
ALT or AST elevation with coagulopathy	
 Discontinue the study treatment immediately
ALT or AST elevation accompanied by symptoms	
 Hospitalize, if clinically appropriate Establish causality
Isolated ALT or AST elevation > 8 × ULN	
 Complete CRFs per liver event guidance*
Jaundice	
 If confirmed, consider interruption or discontinuation of study drug
Isolated ALT or AST elevation > 5 to ≤ 8 × ULN	
 If elevation persists for more than 2 weeks, discontinue the study drug Establish causality Complete CRFs per liver event guidance*
Isolated ALT or AST elevation > 3 to ≤ 5 × ULN (patient is asymptomatic)	
 Monitor liver chemistry tests two or three times weekly
Isolated ALP elevation	
 Repeat liver chemistry tests within 48-72 hours If elevation is confirmed, measure fractionated ALP; if >50% is of liver origin, establish hepatic causality Complete CRFs per liver event guidance*
Any AE potentially indicative of liver toxicity	
 Consider study treatment interruption or discontinuation Hospitalize if clinically appropriate Complete CRFs per liver event guidance*

*Liver event guidance for CRF completion is available in the Site Operations Manual

Table 15-3 Exclusion of underlying liver disease

Disease	Assessment
Hepatitis A, B, C, E	
• IgM anti-HAV; HBsAg, IgM anti-HBc, HBV DNA; anti-HCV, HCV RNA, IgM & IgG anti-HEV, HEV RNA
CMV, HSV, EBV infection	
• IgM & IgG anti-CMV, IgM & IgG anti-HSV; IgM & IgG anti-EBV
Autoimmune hepatitis	
• ANA & ASMA titers, total IgM, IgG, IgE, IgA
Alcoholic hepatitis	
• Ethanol history, GGT, MCV, CD-transferrin
Nonalcoholic steatohepatitis	
• Ultrasound or MRI
Hypoxic/ischemic hepatopathy	
• Medical history: acute or chronic CHF, hypotension, hypoxia, hepatic venous occlusion. Ultrasound or MRI.
Biliary tract disease	
• Ultrasound or MRI, ERCP as appropriate.
Wilson disease	
• Ceruloplasmin
Hemochromatosis	
• Ferritin, transferrin
Alpha-1-antitrypsin deficiency	
• Alpha-1-antitrypsin

16 Appendix 2: Specific Renal Alert Criteria and Actions

Table 16-1 Specific Renal Alert Criteria and Actions

Criteria	Action required
Serum creatinine (sCr) increase 25 – 49% compared to baseline	
 Consider causes and possible interventions Follow up within 2-5 days
Serum creatinine increase > 50%	
 Consider causes and possible interventions Repeat assessment within 24-48h if possible Consider drug interruption or discontinuation unless other causes are diagnosed and corrected Consider hospitalization and specialized treatment
Protein-creatinine or albumin-creatinine ratio increase \geq 2-fold or new onset dipstick proteinuria \geq 1+ or Albumin-creatinine ratio (ACR) \geq 30 mg/g or \geq 3 mg/mmol; or Protein-creatinine ratio (PCR) \geq 150 mg/g or >15 mg/mmol	
 Consider causes and possible interventions Assess serum albumin & serum protein Repeat assessment to confirm Consider drug interruption or discontinuation unless other causes are diagnosed and corrected
New onset glucosuria on urine dipstick (unless related to concomitant treatment, diabetes)	
Assess & document:
 
 Blood glucose (fasting) Serum creatinine Urine albumin-creatinine ratio
New hematuria on dipstick	
Assess & document:
 
 Urine sediment microscopy Assess sCr and urine albumin-creatinine ratio Exclude infection, trauma, bleeding from the distal urinary tract/bladder, menstruation Consider bleeding disorder

Additional specialized assessments are available to assess renal function or renal pathology. (Note: In exceptional cases when a nephrologist considers a renal biopsy, it is strongly recommended to make specimen slides available for evaluation by Novartis to potentially identify project-wide patterns of nephrotoxicity.)

Whenever a renal event is identified, a detailed subject history and examination are indicated to identify, document and potentially eliminate risk factors that may have initiated or contributed to the event:

- Blood pressure assessment (after 5 min rest, with an appropriate cuff size)
- Signs and symptoms such as fever, headache, shortness of breath, back or abdominal pain, dysuria, hematuria, dependent or periorbital edema
- Changes in blood pressure, body weight, fluid intake, voiding pattern, or urine output
- Concomitant events or procedures such as trauma, surgical procedures, cardiac or hepatic failure, contrast media or other known nephrotoxin administration, or other potential causes of renal dysfunction, e.g., dehydration, hemorrhage, tumor lysis

Table 16-2 Follow-up of renal events

Action	Follow up
Assess*, document and record in the Case Report Form (CRF) or via electronic data load. Review and record possible contributing factors to the renal event (co-medications, other co-morbid conditions) and additional diagnostic procedures (MRI etc) in the CRF.	
 • Urine dipstick and sediment microscopy • Blood pressure and body weight • Serum creatinine, electrolytes (sodium, potassium, phosphate, calcium), bicarbonate and uric acid • Urine output
Monitor subject regularly (frequency at investigator's discretion) until:	
 • Event resolution: (sCr within 10% of baseline or protein-creatinine ratio within 50% of baseline) 
or
 
 • Event stabilization: sCr level with $\pm 10\%$ variability over last 6 months or protein-creatinine ratio stabilization at a new level with $\pm 50\%$ variability over last 6 months.

* Urine osmolality: in the absence of diuretics or chronic kidney disease this can be a very sensitive metric for integrated kidney function that requires excellent tubular function. A high urinary osmolality in the setting of an increase in sCr will point toward a “pre-renal” cause rather than tubular toxicity.

17 Appendix 3: Clinically notable laboratory values and vital signs

Table 17-1 Notable Vital Signs And Body Weight

Vital Sign Variable	Notable Criteria
Pulse (beats/min)	>120 bpm Or < 50 bpm
Systolic BP (mmHg)	≥ 160 mm Hg Or ≤ 90 mm Hg
Diastolic BP (mmHg)	≥ 100 mmHg Or ≤ 50 mmHg
Temperature (°C)	>38.3 °C/ 101°F
Body weight (kg)	± 7% from baseline weight

18 Appendix 4: Modified Rankin Scale

MODIFIED RANKIN SCALE (MRS)

Patient Name: _____

Rater Name: _____

Date: _____

Score	Description
0	No symptoms at all
1	No significant disability despite symptoms; able to carry out all usual duties and activities
2	Slight disability; unable to carry out all previous activities, but able to look after own affairs without assistance
3	Moderate disability; requiring some help, but able to walk without assistance
4	Moderately severe disability; unable to walk without assistance and unable to attend to own bodily needs without assistance
5	Severe disability; bedridden, incontinent and requiring constant nursing care and attention
6	Dead

TOTAL (0–6): _____

References

Rankin J. "Cerebral vascular accidents in patients over the age of 60."
Scott Med J 1957;2:200-15

Bonita R, Beaglehole R. "Modification of Rankin Scale: Recovery of motor function after stroke."
Stroke 1988 Dec;19(12):1497-1500

Van Swieten JC, Koudstaal PJ, Visser MC, Schouten HJ, van Gijn J. "Interobserver agreement for the assessment of handicap in stroke patients."
Stroke 1988;19(5):604-7

Commercially Confidential Information

Commercially Confidential Information

Commercially Confidential Information

Commercially Confidential Information

Commercially Confidential Information

Commercially Confidential Information

Commercially Confidential Information

Commercially Confidential Information

20 Appendix 6: Glasgow Coma Scale (GCS)

From: www.glasgowcomascale.org

GLASGOW COMA SCALE : Do it this way

GCS
at 40

EYES
VERBAL
MOTOR

Institute of Neurological Sciences NHS Greater Glasgow and Clyde

CHECK

For factors Interfering with communication, ability to respond and other injuries

OBSERVE

Eye opening, content of speech and movements of right and left sides

STIMULATE

Sound: spoken or shouted request
Physical: Pressure on finger tip, trapezius or supraorbital notch

RATE

Assign according to highest response observed

Eye opening

Criterion	Observed	Rating	Score
Open before stimulus	✓	Spontaneous	4
After spoken or shouted request	✓	To sound	3
After finger tip stimulus	✓	To pressure	2
No opening at any time, no interfering factor	✓	None	1
Closed by local factor	✓	Non testable	NT

Verbal response

Criterion	Observed	Rating	Score
Correctly gives name, place and date	✓	Orientated	5
Not orientated but communication coherently	✓	Confused	4
Intelligible single words	✓	Words	3
Only moans / groans	✓	Sounds	2
No audible response, no interfering factor	✓	None	1
Factor interfering with communication	✓	Non testable	NT

Best motor response

Criterion	Observed	Rating	Score
Obeys 2-part request	✓	Obeys commands	6
Brings hand above clavicle to stimulus on head neck	✓	Localising	5
Bends arm at elbow rapidly but features not predominantly abnormal	✓	Normal flexion	4
Bends arm at elbow, features clearly predominantly abnormal	✓	Abnormal flexion	3
Extends arm at elbow	✓	Extension	2
No movement in arms / legs, no interfering factor	✓	None	1
Paralysed or other limiting factor	✓	Non testable	NT

Sites For Physical Stimulation

Features of Flexion Responses

Modified with permission from Van Der Naalt 2004
Ned Tijdschr Geneesk

For further information and video demonstration visit www.glasgowcomascale.org

Graphic design by Margaret Frey based on layout and illustrations from Medical Illustration 561 - 201002
© 2015 Graham Teasdale 2015

21 Appendix 7: List of prohibited medications

The aim of this document is to provide a specific list of drugs that should not be co-administered with BAF312 because of their CYP2C9/3A4 inhibitory or induction potential.

Due to the constant information arising on drugs, these lists are by no mean exhaustive and medical judgment should always prevail. These lists are adapted to the patient population and the exclusion criteria of the study CBAF312X2207 only.

Only potent CYP2C9 and CYP3A4 inhibitors may have a significant effect on BAF312 exposure and should not be co-administered with BAF312 (Table 21-1).

Potent CYP2C9 and/or CYP3A4 inducers (Table 21-2) should not be coadministered with BAF312 to avoid a potential decrease of efficacy of BAF312 in case of under-exposure due to CYP2C9/CYP3A4 induction (note that topical use is permitted).

Table 21-1 Typical inhibitors of CYP2C9 or CYP3A4

Antibiotics:	Antivirals:
Clarithromycin	Boceprevir
Sulfaphenazole	Telaprevir
Telithromycin	
Troleandomycin	
Protease Inhibitors:	Others:
Indinavir	Amiodarone
Lopinavir	Ataciguat
Nelfinavir	Azapropazone
Ritonavir	Benzbromarone
Saquinavir	Bucolome
Tipranavir	Cobicistat
Antifungals:	Conivaptan
Fluconazole	Elvitegravir
Itraconazole	Mibefradil
Ketoconazole	Nefazodone
Miconazole	Oxandrolone
Posaconazole	Tielinic Acid
Voriconazole	

Table 21-2 **Typical inducers of CYP2C9 and/or CYP3A4**

Aprepitant	Ginkgo	Rifabutin
Avasamide	Lersivirine	Rifampin
Bosentan	Lopinavir	Ritonavir
Carbamazepine	Mitotane	Secobarbital
Dalcetrapid	Modafinil	Semagacestat
Efavirenz	Nafcillin	St. John's wort
Enzalutamide	Nelfinavir	Talviraline
Escalicarbazepine	Nevirapine	Thioridazine
Etravirin	Phenobarbital	Tipranavir
Genistein	Phenytoin	Vigabatrin

**List of abbreviations**

AE	Adverse event
AESI	Adverse event of special interest
aPHE	absolute Perihematoma Edema
ATC	Anatomical Therapeutic Classification
AUC	Area Under the Curve
bid	bis in diem/twice a day
BMI	Body Mass Index
CSR	Clinical Study Report
CT	Computed Tomography
CTCAE	Common Terminology Criteria for Adverse Events
C-SSRS	Columbia-Suicide Severity Rating Scale
DBL	Database Lock
DMC	Data Monitoring Committee
ECG	Electrocardiogram
eCRF	Electronic Case Report Form
	Commercially Confidential Information
FAS	Full Analysis Set
FIR	First Interpretable Results
GCS	Glasgow Coma Scale
HLT	High level terms
i.v.	Intravenous
IA	Interim Analysis
ICH	Intracerebral hemorrhage
	Commercially Confidential Information
MedDRA	Medical Dictionary for Drug Regulatory Affairs
mRS	modified Rankin Scale
NF-L	Neurofilament light
NIBR	Novartis Institute for BioMedical Research
	Commercially Confidential Information
PAS	Pharmacokinetics Analysis Set
PDT	Programming Deliverables Tracker
PHE	Perihematoma Edema
PK	Pharmacokinetics
PPS	Per-Protocol Set
PT	Preferred Terms
p.o.	Oral
PRO	Patient-reported Outcomes
QD	Quaque die / once a day
RAP	Report and Analysis Process
	Commercially Confidential Information
SAE	Serious Adverse Event
SAP	Statistical Analysis Plan
SAS	Statistical Analysis System

SOPs	Standard Operating Procedures
SMQ	Standardized MedDRA Queries
SOC	System Organ Class
TFLs	Tables, Figures, Listings
	Commercially Confidential Information
WHO	World Health Organization

## 1 Introduction

### 1.1 Scope of document

This document details the planned statistical analysis for data collected in the study CBAF312X2207.

Clinical Study Report (CSR) deliverables (tables, figures, listings - TFLs) and further programming specifications are described in separate documents.

This statistical analysis plan (SAP) describes the primary analysis for which a CSR is planned. Interim analyses (IA) may be conducted to support decision making concerning the current clinical study. Nevertheless, a Data Monitoring Committee (DMC) will review unblinded safety and efficacy data on a regular basis and three DMC is planned for this study.

Commercially Confidential Information

### 1.2 Study reference documentation

The SAP is finalized under the amended study protocol version v02 dated on 25-Mar-2019.

The Novartis Institutes for BioMedical Research (NIBR) standard SAP and TLFs shells templates version Final 3.0, 24-Mar-2017 (Effective 3-Apr-2017) and Final 3.0, 04-Jul-2017 (Effective 01-Aug-2017), are respectively used.

The electronic Case Report Form (eCRF) version 5.0 dated on 11-Nov-2019 version is used for TLFs shells development. The DMC charter used for this study is: nibr-BAF312 DMC charter.pdf dated 28-Aug-2020.

### 1.3 Study objectives

The purpose of the study is to investigate the initial efficacy and safety of BAF312 administered on top of standard-of-care compared to placebo in patients with stroke due to ICH; and to determine if the overall clinical profile of BAF312 warrants further clinical development in ICH.

#### 1.3.1 Primary objective

Primary objective	Endpoints related to primary objective	Analysis
To obtain the first efficacy estimate of CCI BAF312 daily (7 days i.v. with titration followed by 7 days p.o.) compared to placebo on reducing absolute perihematoma edema (aPHE) volume on Day 14 after ICH.	aPHE volume measured by CT scan on Day 14 after ICH	

#### 1.3.2 Secondary objective

The secondary objectives are:

Secondary objective(s)	Endpoints related to secondary objective(s)	Analysis

To assess the safety profile of BAF312 in ICH patients.	Continuous assessment of Adverse events (AEs)/Serious AEs during the course of the study (90 days).	Refer SAP section 5.2
To evaluate the pharmacokinetics (PK) of BAF312 in ICH patients.	PK measurements of plasma BAF312 concentrations at 0.5, 2 and 6 h after start of infusion during i.v. titration on Day 1; and before p.o. dosing on Days 8 and 14.	Refer SAP section 5.2 and Section 6

### 1.3.3 Exploratory objective(s)

Commercially Confidential Information

Commercially Confidential Information

## 1.4 Study design and treatment

This is a randomized, patient- and investigator-blinded, placebo-controlled, parallel group study of BAF312 (siponimod) on top of standard-of-care for intracerebral hemorrhage (ICH), consisting of 3 epochs: **Screening/Baseline, Treatment, and Follow-Up** as indicated in [Figure 1-1](#).

Commercially Confidential Information

Approximately 33 patients per treatment group (~65 patients in total) will be randomized, with an expected drop-out rate of approximately 10% to obtain at least 60 completed study subjects (Day 14). Patients will be assigned to one of the following 2 treatment arms, BAF312 or Placebo, in a ratio of 1:1.

Reduction of perihematoma edema (PHE) measured by CT imaging at 14 days after ICH is the primary endpoint for measuring BAF312 efficacy in this study.

Regular DMC will occur in order to provide recommendations to the sponsor to continue the trial according to the protocol and any relevant amendments, or to make changes or adjustments to the study.

## 2 First interpretable results (FIR)

Commercially Confidential Information

Commercially Confidential Information

### **3 Interim/DMC analyses**

Commercially Confidential Information

Commercially Confidential Information

## Commercially Confidential Information

## 4 Statistical methods

### 4.1 Analysis sets

**All randomized subjects:**

They correspond to all patients included in the study who fulfilled the inclusion/exclusion criteria.

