11.1 Analysis sets

The Full Analysis Set will include all patients who are randomized and received at least one dose of study drug after randomization.

The Safety Analysis Set will include all patients that received at least one dose of study drug.

The Per Protocol Set (PPS) will include all patients in the full analysis set (FAS) having received at least the first infusion on Day 1 and no protocol deviations with relevant impact on efficacy data.

The PK Analysis Set will include all patients with at least one available valid (i.e., not flagged for exclusion) PK concentration measurement, who received any study drug and experienced no protocol deviations with relevant impact on PK data.

For all analysis sets, patients will be analyzed according to the study treatment(s) received.

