**Full Analysis Set (FAS):**

The FAS will include all patients who are randomized and received any amount of study drug.

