**PK Analysis Set (PAS):**

The PAS will include all patients with at least one available valid (i.e., not flagged for exclusion) PK concentration measurement, who received any study drug and experienced no protocol deviations listed in table 4.1 with relevant impact on PK data.

For all analysis sets, patients will be analyzed per the study treatment(s) received.

All listings will use Randomized patients.

Frequency counts and percentages (using FAS as denominator) of patients in each of the above defined analysis sets will be summarized. In addition, listings of patients excluded from each of the analysis sets will be provided.

The analysis sets and protocol deviation are related to this study as follows:

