### 8.2 Descriptive analyses

#### Subject demographics and other baseline characteristics

The FAS will be used for all patient demographic and baseline characteristic summaries and listings, unless otherwise specified.

All data for background and demographic variables will be listed by treatment and patient. Summary statistics will be provided by treatment. Descriptive statistics, frequency counts and percentages will be tabulated by treatment arm, as appropriate.

Baseline demographic includes following,

- Age (in years)
- Age category in years (<70; >=70)
- Sex (Male, Female)
- Race (Caucasian, Black, Asian, Native American, Pacific Islander, Unknown, Other)
- Ethnicity (Hispanic or Latino, East Asian, Southeast Asian, South Asian, West Asian, Russian, Mixed Ethnicity, Not Reported, Unknown, Other)
- Weight (kg)
- Height (cm)
- Body Mass Index (BMI) – calculated as  $\text{weight (kg)} / (\text{height (m)})^2$

Other baseline characteristics includes,

- Glasgow Coma Scale (GCS) total score
- GCS total score in categories (<13 a.u., >=13 a.u.)
- Baseline blood pressure includes systolic (mmHg), diastolic (mmHg), pulse (Beats/min), and Temperature (°C)

Commercially Confidential Information

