### **Patient disposition**

The FAS will be used for the patient disposition summaries. The summary by treatment arm will show:

- Number (%) of randomized patients who were not treated;
- Number (%) of randomized patients who were treated;
- Number (%) of patients who completed the study treatment;
- Number (%) of patients who discontinued the study treatment;
- Reasons for study treatment discontinuation.

Frequency counts and percentages of patients for each of analysis set will be presented separately by treatment. Any protocol deviation (selection criteria not met, patient not withdrawn as per protocol, key procedures not performed as per protocol, treatment deviation, prohibited concomitant medication, other Good Clinical Practice (GCP) deviation) will be tabulated by the deviation type and treatment.

All protocol deviations will be presented in a listing by treatment and patient. Summary of protocol deviation with categories will be presented by treatment.

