### **Deaths**

Deaths will be summarized by primary system organ class and preferred term by treatment. Listing of all death will be produced for patient who signed informed consent and randomized.

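### Disposition is summarised on a set that contains only dosed patients, and the randomised set is defined by eligibility instead of by randomisation

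*SAP*

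**What the plan says.** **Randomised set.** SAP 4.1, under All randomized subjects, says: "They correspond to all patients included in the study who fulfilled the inclusion/exclusion criteria". Randomisation itself is not part of the definition. At the end of the same section comes a general rule: "All listings will use Randomized patients".

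**FAS.** SAP 4.1: "The FAS will include all patients who are randomized and received any amount of study drug". Protocol 11.1 agrees in substance: "The Full Analysis Set will include all patients who are randomized and received at least one dose of study drug after randomization". Neither sets an eligibility condition; both require dosing.

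**Disposition.** SAP 8.2, Patient disposition: "The FAS will be used for the patient disposition summaries". The first row of that table is "Number (%) of randomized patients who were not treated". SAP 4.1 also takes the FAS as the denominator for the counts of patients in each analysis set.

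**Ineligible patients.** The PPS is a subset of the FAS, and SAP Table 4-1 removes patients with eligibility deviations from it. The PK set uses the same exclusions, except for the item on prohibited medication.

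**Listings with their own population.** For demographics and baseline: "The FAS will be used for all patient demographic and baseline characteristic summaries and listings, unless otherwise specified". For deaths: "Listing of all death will be produced for patient who signed informed consent and randomized". SAP section 8 opens by placing its safety analyses on the Safety Set. SAP 6.3 lists PK data on all randomised subjects and flags those excluded from the PK analysis.

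**The concern.** There are two separate faults. The first is a table whose population rules out one of its own rows: a set restricted to dosed patients cannot count undosed ones. The second is a set named for randomisation but defined by eligibility, in a plan that elsewhere expects some randomised patients to be ineligible.

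What is at stake is the record of patient flow. The primary analysis uses the PPS. Table 4-1 leaves the clinical team some discretion over which eligibility deviations count, and the final set assignment is documented after database lock because one criterion needs unblinded information. A reader therefore needs to see, by arm, who was randomised, who was never dosed, and who was removed and why.

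**Working it through.** The plan gives no figure on this point to reproduce. The check is set logic on the SAP's definitions, with an illustration based on the planned total of about 65 randomised patients (SAP 1.4).

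**1. Disposition.** Let R be all patients assigned a randomisation number and D all dosed patients.

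- FAS = R and D.
- Undosed row, counted within the FAS = (R and not D) and (R and D) = empty. The count is 0 (0%), whatever happens in the trial.
- Treated row within the FAS = 100%.

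Suppose u of 65 randomised patients are never dosed. The value of u is an assumption. The drop-out rate of about 10% in SAP 1.4 concerns completion to Day 14, so it does not supply one.

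| u | FAS = 65 − u | Undosed row on the FAS | Undosed row on R = u/65 |
|---|---|---|---|
| 1 | 64 | 0 of 64 (0%) | 1 of 65 (1.5%) |
| 2 | 63 | 0 of 63 (0%) | 2 of 65 (3.1%) |
| 3 | 62 | 0 of 62 (0%) | 3 of 65 (4.6%) |
| 5 | 60 | 0 of 60 (0%) | 5 of 65 (7.7%) |

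If a programmer took the numerator from R but kept the FAS denominator, u = 2 would give 2/63 = 3.2% undosed beside 63/63 = 100% treated. These do not add up to a whole.

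**2. Analysis-set counts.** Suppose also that k dosed patients are ineligible and that all undosed patients are eligible. The literal randomised set then holds 65 − k patients, reported as (65 − k)/(65 − u) of the FAS.

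- u = 2, k = 0: 65/63 = 103.2%.
- u = 0, k = 2: 63/65 = 96.9%.
- u = 2, k = 2: 63/63 = 100%, although each set lacks two patients that the other contains.

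**3. Randomised set against the PPS rule.** Table 4-1 has work to do only if ineligible patients can be in the FAS. FAS membership requires randomisation. So the SAP treats some ineligible patients as randomised, while the definition of All randomized subjects leaves them out. As worded, the FAS is not a subset of the randomised set.

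**4. Which listings are affected on the literal reading.**

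| Listing | Population stated | Ineligible dosed patients |
|---|---|---|
| PK concentrations (SAP 6.3) | All randomised subjects | Omitted, though it is meant to flag patients excluded from the PK analysis |
| Set exclusions (SAP 4.1); protocol deviations (SAP 8.2) | None of their own, so the general rule applies | Omitted by the general rule, yet called for by the listing's own purpose |
| AEs and SAEs (SAP 8.2) | General rule says randomised; section 8 says Safety Set | Unclear: two rules conflict |
| Demographics and baseline (SAP 8.2) | FAS | Included |
| Deaths (SAP 8.2) | Consented and randomised | Included; no eligibility condition |

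**5. Effect on efficacy results.** None. The PPS removes eligibility deviations under its own rule, the FAS used for sensitivity is defined separately, and the sample size calculation does not depend on these definitions.

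**The case against.** The strongest reply is that the randomised-set wording is loose drafting. Protocol 6.5 has patients randomised once they meet all criteria, and Protocol 4.2 bars enrolment on any deviation from them. On that view the SAP sentence merely separates randomised patients from screen failures. The PPS rule would be pointless if only truly eligible patients counted as randomised, so the intent is probably sound. This stands as an account of intent. It does not rescue the text, because Table 4-1 plans for the patients that the definition excludes.

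A reader might infer that ineligible patients disappear from every listing. The documents do not support that. Demographic and baseline listings use the FAS, and deaths have their own wording. The section on safety points to the Safety Set. Listings of all deviations and of patients excluded from each set are explicitly planned. The omission is clear only for listings tied to the randomised set, with PK as the plain case.

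Nor do the documents support an inference that undosed patients are being concealed. The explicit row shows that the sponsor means to count them, and an eligible undosed patient should appear in the listing of exclusions from the FAS. What is lost is the count by arm in the two summary tables.

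Finally, SAP 1.1 puts table, figure and listing specifications in separate documents, which may assign different populations. That is possible and cannot be checked here; it would leave those specifications in conflict with the SAP.

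**Conclusion.** The point holds as a fault in the reporting of patient flow. The disposition finding is certain: with the FAS as population, the undosed row is always 0 and the treated row always 100%. The analysis-set percentages have the same weakness, because they share the FAS denominator. The definition of All randomized subjects is wrong as worded and contradicts the PPS rule. Its consequence is limited to listings based on the randomised set, and is unresolved for AEs and SAEs.

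The size in patients is unknown, since the documents give no rate of undosed or ineligible randomised patients. The figures for u and k are illustrations only. No efficacy estimate, interval, p-value or power figure moves.

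**What to change.** 1. In SAP 4.1, define All randomized subjects as every patient assigned a randomisation number, regardless of eligibility or dosing.
2. Use that set as population and denominator for the disposition table in SAP 8.2 and for the analysis-set counts in SAP 4.1. Present both by assigned arm: SAP 4.1 analyses all sets by treatment received, and an undosed patient has received none.
3. Use it for the listings that refer to randomised patients, including PK, protocol deviations and set exclusions.
4. Reconcile the general listing rule in SAP 4.1 with the Safety Set statement that opens section 8 and with the FAS rule for demographic and baseline listings, so that each listing has one stated population. The FAS can stay for the baseline summaries.

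The cost is a few sentences in SAP 4.1 and section 8 and a changed population flag in programming, made before database lock. No new data are needed, because Protocol 10.3 already tracks randomisation codes in the IRT.
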